1.0 Study Summary

Study Title	Activity, Adiposity, and Appetite in Adolescents 2 (AAAA2)
Study Design	Cross-sectional
Primary Objective	To examine the association between physical activity and appetite control in adolescents, with metabolic function serving as a mediator.
Secondary Objective(s)	n/a
Research Intervention(s)/ Investigational Agent(s)	n/a
IND/IDE #	n/a
Study Population	Adolescents age 14-17 (Tanner Stage III-V)
Sample Size	Approximately 60 (40 completing the entire protocol)
Study Duration for Individual Participants	Approximately 35 days (this can be extended to accommodate participant's schedules)
Study Specific Abbreviations/ Definitions	RD – registered dietitian, MS – measurement session, EE – energy expenditure, EI – energy intake, DXA – dual energy X-ray absorptiometer, EGC – Hyperinsulinemic-Euglycemic Clamp, CRF – Cardiorespiratory fitness, RMR – resting metabolic rate, TEF – thermal effect of feeding, CEQ – control of eating questionnaire, VAS – visual analogue scale, FM – fat mass, FFM – free fat mass, CCHLN – Center for Children's Healthy Lifestyles and Nutrition, CRF – cardiorespiratory fitness

2.0 Objectives

- 2.1 To examine the association between physical activity and appetite control in adolescents, with metabolic function serving as a mediator.
- 2.2 Hypothesis 1: Appetite, as measured subjectively, via self-reported hunger and palatability responses, and, objectively, via satiety/appetite hormones (glucose, insulin, ghrelin, and leptin) responses following a standardized meal and calories consumed during ad libitum meal, will be altered in sedentary vs. active adolescents, regardless of body weight status.

Hypothesis 2: Reduced metabolic function, defined as low insulin sensitivity and metabolic flexibility, measured by hyperinsulinemic euglycemic clamp and indirect calorimetry, will be associated with poorer appetite control and physical inactivity as defined in Hypothesis 1.

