Challenges to Existing Paradigms. The status quo as it pertains to appetite control emphasizes the role of peripherally derived signals mediating energy intake in the CNS [Figure 7 - e.g. insulin and ghrelin mediate appetite through pathways centered in the hypothalamus [45-47]]. This concept is supported by a strong body of evidence, dating from as far back as 50 years, including the discovery of leptin in 1994. However, it has been argued that this paradigm primarily accounts for the inhibition of eating as opposed to the drive of eating. An alternative approach, centered on the concept of energy balance, postulates that daily energy expenditure regulates appetite (Figure 7). It has been put forth by Mentor [name], and adopted by others [20, 22], that overall appetite is regulated through three components: 1) a tonic (i.e. constant) drive for food driven by energy demands; 2) tonic inhibition from signals of energy storage (e.g. leptin); 3) episodic (i.e. response-initiated) signals from the periphery in response to food. This new approach emphasizes the contribution of physical activity and energy expenditure on both the tonic excitatory drive to eat and episodic regulation of fasting hormones (ghrelin) and satiety hormones (GLP-1 and PYY) [19, 48, 49]. Importantly, this new formulation recognizes the role of resting metabolic rate [16] and fat free mass on appetite control. We extend this theory to include metabolic function, as there is evidence that it is also associated with eating behavior (see section A.2.), pointing to a specific biological mechanism by which appetite regulation may occur.

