3.3 **New Approaches.** The proposed research is innovative because it shifts beyond the tonic inhibition approach, to include the regulation of appetite via energy expenditure and metabolic function. Our preliminary studies (see sections 2.1-2.5) indicate that energy intake and disinhibition become dysregulated at low levels of physical activity, resulting in 3.8 fold greater fat mass 1 year later [50]. We will extend previous findings in adults to adolescents, a previously unexamined population in regard to this concept. Additionally, we have expanded upon previous studies in the proposed project by exploring plausible metabolic mechanisms that underlie appetite dysregulation at low levels of activity. By completing this work, it is our expectation that we will have described the independent effects of physical activity and obesity on appetite and energy metabolism in adolescents.

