 - **TFEQ**
 - **CEQ**
 - **VAS Pre-Meal**
 - **VAS Post-Hedonic**
 - **VAS**
- **Anthropometry and Body Composition via DXA.**
 - Fat mass (FM) and fat-free mass (FFM) will be measured using a whole-body dual energy X-ray absorptiometer (DXA, Lunar DPX system, version 3.6).
- **Waist and Hip Measurements.** Waist measured in centimeters, two inches above the umbilicus at skin level, at the end of a normal breath expiration, with arms relaxed at sides. Hip measured in centimeters at the maximum circumference of the buttocks, with arms relaxed at the sides.

- **Fixed/*Ad libitum* Meals.** Appetite (see below) will be assessed following a fixed standard breakfast (40% of RMR, composed of 55% carbohydrate, 15% protein, 30% fat). Food intake (total kcals) will also be assessed using an *ad libitum* meal served three hours after the fixed meal. Participants will be instructed to eat until comfortably full and informed that they can request more of the meal at any point.
- Each plate of food will be weighed before and after serving, without the subjects' knowledge.
- **Appetite and Eating Behavior** Subjective assessment of hunger and palatability will be completed using self-rated visual analogue scales (VAS) [51], with each scale consisting of a 10-cm long line separating statements such as "not at all hungry" and "extremely hungry". [VAS tools are widely used to assess health conditions and show good test-retest reliability [52], especially in within-subject repeated measures study designs [53].] Perceptions of dietary restraint, disinhibition, and hunger will be measured during each measurement session using the Three Factor Eating Questionnaire (TFEQ) [54]. The Control of Eating Questionnaire (CEQ) will be used to assess hunger, fullness, cravings, the desire to eat certain types of foods, and the ability to resist urges to eat [55]. Objective assessment of appetite will be completed using blood samples taken from an indwelling catheter, and analyzed for episodic regulation of the following fasting and satiety hormones: glucose, insulin, leptin, ghrelin, glucagon-like peptide 1 (GLP-1), and peptide YY (PYY). All samples will be mixed a standard preservative (400 μ L of 10,000 KIU aprotinin), centrifuged, the plasma divided and stored in -80°C freezer until later analysis.

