19.0 Data Management and Confidentiality

19.1 **Statistical Analysis Plan.** To address Aim 1, we will compare groups (active vs. sedentary, normal weight vs. overweight/obese) using mixed models (linear or generalized, as appropriate) that adjust

SHORT TITLE:

for clustering of time points within person. For VAS appetite measures, which are assessed at multiple time points within a single measurement session, we will conduct analyses in two ways. First, we will conduct between group analyses using each of the seven individual assessments (e.g. 60 min post-meal) to see if the values differ by physical activity or body weight group. Second, we will also calculate area under the curve (AUC) for each variable of interest (e.g. hunger, ghrelin), and test for group differences on that measure using a linear or generalized regression model. To address Aim 1, hypothesis 2, we will repeat the analyses described above and include insulin sensitivity as a covariate.

- 19.2 The sample size was determined by a review of similar studies indicating a range of 12-44 participants.
- 19.3 All study staff will complete research training, save study documents on drives that require authorization of access, password protection, or encryption. Paper study documents will be protected using physical controls (such as being kept in secured locked offices in locked file cabinets). Study staff will keep identifiers separate from study IDs and data [master list]) during storage, use, and transmission.
- 19.4 A Certificate of Confidentiality has been issued for this study. Certificates are automatically issued for NIH funded research per [NIH policy](#).
- 19.5 Study surveys will use a study ID for an identifier, study staff will lock documents in secure office locations and keep data collection surveys and instruments with them at all times when in use.
- 19.6 Describe how data or specimens will be handled study-wide:
 - Study ID and visit date will be included on source documentation
 - Study documents will be stored in secure offices in secure file cabinets, Redcap, the W drive, or BOX (the study team has previous approval to use).
 - Study source documentation and other data will be kept at least 3 years after submission of the Final Progress Report to the NIH.
 - The CMH study team, other approved staff members from approved organizations (KUMC, etc), the sponsor (NIH), the IRB.
 - The study lab coordinator, the PI.

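### Hypothesis 1 treats leptin as a meal response and omits GLP-1 and PYY, against the protocol's own classification; with no fat-mass adjustment, a fat-mass difference within a weight category could appear as an activity effect on leptin

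*Combined protocol and SAP*

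**What the plan says.** Hypothesis 1 (2.2) names four blood markers as "satiety/appetite hormones (glucose, insulin, ghrelin, and leptin) responses following a standardized meal" and predicts that appetite "will be altered in sedentary vs. active adolescents, regardless of body weight status".

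The Background (3.0, paragraph on challenges to existing paradigms) sets out a three-part model of appetite. Leptin belongs to the second part, and food-initiated signals are a separate third part: "tonic inhibition from signals of energy storage (e.g. leptin); 3) episodic (i.e. response-initiated) signals from the periphery in response to food". The same paragraph then refers to "episodic regulation of fasting hormones (ghrelin) and satiety hormones (GLP-1 and PYY".

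Section 6.0 (Appetite and Eating Behavior) assays "glucose, insulin, leptin, ghrelin, glucagon-like peptide 1 (GLP-1), and peptide YY (PYY" and introduces all six as markers of episodic regulation.

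For the analysis, 19.1 states that "we will compare groups (active vs. sedentary, normal weight vs. overweight/obese) using mixed models". It also tests group differences in AUC for each variable of interest, without saying whether AUC is total or baseline-corrected. The only covariate it names is insulin sensitivity, for Hypothesis 2. DXA fat mass is collected (6.0) but 19.1 does not use it. Section 3.3 expects the study to have "described the independent effects of physical activity and obesity on appetite and energy metabolism in adolescents".

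**The concern.** There are two linked problems.

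The first is consistency. The hypothesis leaves out the two hormones that the protocol's theory names as satiety signals. It includes as a meal response a hormone that the same theory assigns to energy storage.

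The second is interpretation. If leptin reflects fat stores, as the Background says, a sedentary group with more fat mass than the active group in the same weight category would tend to have higher leptin even if its response to the meal were identical. Hypothesis 1 gives no direction for the alteration, so higher leptin could be read as supporting it. At stake is the separation of activity from obesity that 3.3 promises, for this one marker.

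**Working it through.** **Step 1: the marker lists side by side.**

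| Analyte | 2.2, Hypothesis 1 | 3.0, Background | 6.0, Procedures |
|---|---|---|---|
| Glucose, insulin | meal response | not placed in the three-part model | assayed, episodic |
| Ghrelin | meal response | fasting hormone, episodic | assayed, episodic |
| Leptin | meal response | tonic, energy storage | assayed, episodic |
| GLP-1, PYY | not listed | satiety hormones, episodic | assayed, episodic |

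Hypothesis 1 names 4 of the 6 assayed markers; 6 - 4 = 2 are missing. Leptin's class in 3.0 conflicts with both 2.2 and 6.0.

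**Step 2: what the design controls.** Sections 4.1, 6.1 and 12.1 plan 10 participants in each of four activity-by-weight cells: 4 x 10 = 40, or 20 active and 20 sedentary. With equal cells, a difference between weight categories cannot create a leptin difference between activity groups. Only a fat-mass difference inside a category can.

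The Background makes such a difference plausible without giving its size. It reports that the least active adults gained the most fat mass, and it cites an adolescent exercise study in which body composition improved while body weight did not change.

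**Step 3: what AUC carries.** Write leptin at time t as a fasting level L plus a meal-related change m(t), over the 3 hours of sampling (6.5).

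- Total AUC = 3L + area under m.
- Baseline-corrected AUC = area under m.

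If two groups differ by δ in L and share the same m, total AUC differs by 3δ and baseline-corrected AUC by 0. If the meal-related change itself scales with the fasting level, some difference remains after correction. Because 19.1 does not state the type, the result could go either way.

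**Step 4: size, under assumptions.** The plan gives no alpha, power, effect size or SD, so it has no figure to reproduce. The inputs below are assumptions except for the cell sizes:

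- 10 per cell (12.1); two-sided 0.05; linear regression on activity and weight category.
- Within a category, fat mass (FM) has SD 1, and leptin = ρ·FM + √(1 - ρ²)·error, so leptin also has SD 1. ρ is 0.6 or 0.8.
- Sedentary minus active fat mass within a category is d = 0 to 1 SD.
- Activity has no direct effect on leptin.

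Rate at which activity is declared associated with leptin (6,000 simulated studies per row and ρ):

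| d (SD) | Weight category only, ρ = 0.6 | Weight category only, ρ = 0.8 | Fat mass added, ρ = 0.6 / 0.8 |
|---|---|---|---|
| 0 | 5.2% | 5.5% | 5.2% / 5.5% |
| 0.25 | 7.4% | 9.4% | 5.3% / 4.7% |
| 0.5 | 15.8% | 22.6% | 4.8% / 5.1% |
| 0.8 | 32.1% | 49.2% | 4.7% / 5.0% |
| 1.0 | 45.1% | 69.3% | 5.0% / 4.6% |

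**Step 5: cross-check by formula.** The expected activity difference in leptin is ρd, with standard error √(2/20) = 0.316. The rate is approximately Φ(ρd/0.316 - 1.96).

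- d = 0.5, ρ = 0.6: 0.30/0.316 = 0.95, Φ(-1.01) = 15.6%.
- d = 0.5, ρ = 0.8: 0.40/0.316 = 1.26, Φ(-0.70) = 24.4%.
- d = 1.0: 47.5% and 71.6%.

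These agree with the table to within about 2.5 percentage points. The formula ignores the t distribution's heavier tails.

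The rates are false positives for a *direct* activity effect. As a statement of total association, a leptin difference that arises through fat mass would be real.

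**The case against.** The strongest reply is that weight status is already a design factor, and Hypothesis 1 claims independence from weight status, not from fat mass. This stands in part. A reader might infer that adiposity is uncontrolled altogether, but the balanced 2x2 cells rule that out. What remains is the within-category difference, and 3.3 speaks of obesity's independent effect, which a two-level weight category captures only coarsely.

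Three further inferences are tempting and unsupported.

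- *A leptin difference alone would confirm Hypothesis 1.* No section says so. The hypothesis also covers hunger, palatability, the other blood markers and ad libitum intake, and no decision rule is stated.
- *GLP-1 and PYY are excluded from analysis.* They are not. Section 6.0 assays them as objective measures of appetite, and the AUC list in 19.1 is open. They are missing from the stated hypothesis, and that omission does not cause the leptin problem.
- *Taking leptin out of the meal-response set would bring 2.2 into line with 6.0.* It would not, because 6.0 also calls leptin episodic. Both sections need attention.

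Two other points are fair. Tonic inhibition is itself one of the protocol's three components of appetite regulation, so leptin belongs in the study; the issue is its role as a meal response. Fat mass may also lie on the path from activity to leptin, in which case adjustment changes the question from total to direct association. That is a reason to report both contrasts.

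**Conclusion.** The inconsistency across 2.2, 3.0 and 6.0 is certain from the text. The route from within-category fat mass to an apparent activity effect on leptin is open, because 19.1 neither adjusts for fat mass nor fixes the AUC type. Its size is unknown. It is negligible if fat mass is equal within categories. Under the assumed correlation of 0.6 to 0.8, the false-positive rate is 16-23% at a 0.5 SD difference and 45-69% at 1 SD, and about 5% once fat mass is in the model. These figures apply to fasting leptin or a measure that carries it, such as total AUC; a baseline-corrected AUC would remove much of the effect. The point concerns one of the four named markers and does not invalidate Hypothesis 1 as a whole. It should be corrected before analysis.

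**What to change.** In 2.2, add GLP-1 and PYY to the meal-response set. Reconcile leptin's class across 2.2, 3.0 and 6.0 so that each section describes it in the same way.

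In 19.1:

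- Analyse leptin separately as a fasting tonic marker.
- Report its activity contrast both unadjusted and adjusted for DXA fat mass. Name the scan used; the one at Measurement Session 1 is from the same visit as the meal test.
- Base any claim of an effect independent of adiposity on the adjusted contrast only.
- State for every hormone whether AUC is total or baseline-corrected.

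The cost is wording in 2.2, 6.0 and 19.1 and one extra model. No new sample, assay or visit is needed, since all six analytes and DXA fat mass are already planned. The downsides are two more markers named in the hypothesis, and an adjusted contrast that is a direct association and may remove a genuine path from activity through fat mass to leptin.

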3.0 Background

3.1 Overall Scientific Premise- Weight gain is determined by energy balance status. Data from the National Health and Nutrition Examination Survey (NHANES) indicate that 16.9% of US children and adolescents are classified as obese (BMI $> 95^{\text{th}}$ percentile) and 31.8% of youth are either overweight or obese (BMI $> 85^{\text{th}}$ percentile) [1, 2]. This is driven, in part, by declines in physical activity that begin around age 15 years for boys and age 10-13 years for girls [3], with only 27% of 12-17 year olds obtaining 60 minutes of moderate to vigorous physical activity [4]. Healthy eating follows a similar same age-related decline, but at an even lower level with only 10% eating five servings of fruits/vegetables per day [5]. At the most basic level, obesity is the result of a mismatch between the amount of calories consumed and the amount of calories expended over an extended period of time. In reality a variety of known and unknown systems involving complex relationships between biological, physiological, psychosocial, and environmental factors [6, 7] influence the components of energy balance [8, 9]. Clearly, if effective prevention and treatment strategies currently existed based on a complete understanding of energy balance, worldwide levels of obesity would not have reached pandemic proportions [10].

Physical Activity is Associated with Appetite Control. The concept of dysregulation of appetite at low levels of physical activity is not new, with Mayer and others [11, 12] exploring the topic in a series of studies in the 1950s. It was observed in mice, rats, and humans [13-15] that energy intake only increased proportionally with energy expenditure within a certain range of physical activity, described by Mentor [name] [16] as the ‘zone of regulation’ (Figure 2). In contrast, when activity levels are low (inactivity), the relationship between intake and expenditure is uncoupled and in the “non-regulated zone”, resulting in energy imbalance.

3.2 Recent work has confirmed the links between elevated energy intake and appetite dysregulation at low levels of physical activity. We ([name] and [name], among others) recently completed an analysis of energy balance among adults (N=421, mean age=28 years) over a 12-month period which included grouping participants by quintiles according to their level of objectively measured physical activity [17]. First, we observed increasing levels of physical activity in quintiles 2-5 corresponded with increases in energy intake, indicating energy balance. However, individuals in the lowest quintile of physical activity had a higher energy intake than groups 2 and 3, despite expending less energy (Figure 1). Second, individuals in this lowest quintile of physical activity had higher levels of disinhibition and preference for savory foods compared to their more active peers. Third, individuals with low levels of physical activity experienced the largest gains in fat mass, resulting in 3.8 higher risk of gaining clinically significant ($>3\%$) amounts of fat

[figure not shown]

Figure 2. Mayer et. al 1956 found energy intake became uncoupled at low levels of activity, described by [name] 2011 as the ‘non-regulated zone’.

mass over 1-year. Our findings have since been replicated by others [18-20]. Taken together, our results support the hypothesis proposed by Mayer *et al.* [15] and others that a low level of physical activity is a risk factor for weight gain via a link to not only reduced energy expenditure but also dysregulated appetite control which leads to gains in fat mass. However, these findings raise important unanswered questions. What are the biological mechanisms by which physical activity influences appetite? What is the temporal relationship between physical activity and appetite control? Are the links observed in adults also present in adolescents?

Evidence that Metabolic Function be a Mediator. As noted by [name]

metabolic phenotype described in this section, but it is unknown if this is associated with appetite dysregulation and subsequent weight gain. Conversely, it is well known that increasing physical activity obtained through structured exercise will improve systemic metabolic function [37-39], but it is not clear if this will also improve appetite regulation.

Appetite Control in Adolescents is Unknown. Despite a growing body of evidence in adults that physical activity plays a role in mediating appetite control, little work has been performed in adolescents. Most studies in adolescents consists of appetite measures performed as secondary outcomes in studies with possible confounding factors (e.g. underlying disease risk) [39-41]. Observational data suggests higher levels of obesity are associated with dysregulated appetite as defined by satiety and responses to food cues [42] and higher energy intake despite lower levels of physical activity [43]. A smaller number of clinical trials have found that exercise trials in adolescents improves biomarkers of appetite control [44]. Of particular note is an eight-month aerobic intervention among OW/OB adolescents, with the effects of exercise isolated since there were no changes in body weight (but improvements in body composition) during the study [37]. Hormones peptide YY and resistin decreased following completion of the intervention, suggesting improved regulation of appetite with higher levels of physical activity. However, assessments in each of these studies were limited to fasted measurements, not as part of a more methodologically rigorous and informative meal challenge. Taken together, a small number of studies in adolescents support the scientific premise that physical activity and appetite are associated. What is not clear is strength of the association between the activity and appetite, the role of metabolism in this relationship, nor the effects of a structured exercise regimen in this association.

Challenges to Existing Paradigms. The status quo as it pertains to appetite control emphasizes the role of peripherally derived signals mediating energy intake in the CNS [Figure 7 - e.g. insulin and ghrelin mediate appetite through pathways centered in the hypothalamus [45-47]]. This concept is supported by a strong body of evidence, dating from as far back as 50 years, including the discovery of leptin in 1994. However, it has been argued that this paradigm primarily accounts for the inhibition of eating as opposed to the drive of eating. An alternative approach, centered on the concept of energy balance, postulates that daily energy expenditure regulates appetite (Figure 7). It has been put forth by Mentor [name], and adopted by others [20, 22], that overall appetite is regulated through three components: 1) a tonic (i.e. constant) drive for food driven by energy demands; 2) tonic inhibition from signals of energy storage (e.g. leptin); 3) episodic (i.e. response-initiated) signals from the periphery in response to food. This new approach emphasizes the contribution of physical activity and energy expenditure on both the tonic excitatory drive to eat and episodic regulation of fasting hormones (ghrelin) and satiety hormones (GLP-1 and PYY) [19, 48, 49]. Importantly, this new formulation recognizes the role of resting metabolic rate [16] and fat free mass on appetite control. We extend this theory to include metabolic function, as there is evidence that it is also associated with eating behavior (see section A.2.), pointing to a specific biological mechanism by which appetite regulation may occur.

3.3 **New Approaches.** The proposed research is innovative because it shifts beyond the tonic inhibition approach, to include the regulation of appetite via energy expenditure and metabolic function. Our preliminary studies (see sections 2.1-2.5) indicate that energy intake and disinhibition become dysregulated at low levels of physical activity, resulting in 3.8 fold greater fat mass 1 year later [50]. We will extend previous findings in adults to adolescents, a previously unexamined population in regard to this concept. Additionally, we have expanded upon previous studies in the proposed project by exploring plausible metabolic mechanisms that underlie appetite dysregulation at low levels of activity. By completing this work, it is our expectation that we will have described the independent effects of physical activity and obesity on appetite and energy metabolism in adolescents.

